### **3.8. Sample Size Estimation**

The primary outcome, suicide ideation, will be assessed up to 4 times: baseline, 2 weeks, 26 weeks, and 52 weeks). We will analyze data from the full sample and also conduct separate analyses for two subgroups of interest: those with suicide ideation at baseline and those without suicide ideation at baseline. Our primary planned analyses entail slope comparisons for suicide ideation scores.

Our assumptions for sample size estimation were based on previous research conducted by our team. In two separate pilot studies of our two-week treatment program, 50-70% of participants reported suicide ideation at baseline. We used this range to estimate the percentage of participants expected to report suicide ideation at baseline. We also based estimates on the results of a published RCT comparing the CRP to treatment as usual (Bryan et al., 2017a), which found small to moderate differences in suicide ideation between treatment groups over time ( $0.3 < d < 0.7$ ). We used this range to estimate a lower bound for the anticipated effect size (i.e.,  $d=0.3$ ).

Assuming a two-tailed  $\alpha < .05$ , a within-between interaction (i.e., treatment x time), a small correlation ( $r=0.1$ ) among repeated measures, a sample size of 112 ( $n=66$  per group) provides 80% power to detect an effect size equivalent to  $d=0.3$ . To account for expected attrition (~25%) and missing data (participants completing only 3 of 4 scheduled assessments), we will aim to enroll a total of  $N=150$  ( $n=75$  per arm) eligible participants, which provides 86% power to detect an effect size equivalent to  $d=0.3$ . Assuming two-thirds of the sample report suicide ideation at baseline—a rate comparable to our pilot studies—we will have 80% power to detect a minimum effect size of  $d=0.38$  among participants endorsing suicide ideation at baseline. Because we expect to consent and screen approximately 5 veterans to identify each eligible participant who consents to treatment, we will therefore enroll a total of 750.

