## 4.3. Ecological Momentary Assessment

EMA assessments will be programmed and collected using MetricWire, a HIPAA-compliant EMA program that can coordinate sending mass text and email queries within a predetermined time-window. MetricWire collects de-identified responses using subject ID numbers. The program pushes assessment notifications to each subject's smartphone. Subject responses are then submitted to an encrypted server. MetricWire can automatically respond to invalid responses (e.g., numeric values outside the range of possible responses), filter multiple responses, and send standardized information to subjects based on predetermined response criteria (e.g., sending crisis hotline information for subjects indicating severe suicide ideation). Subjects will receive 4 EMA prompts per day on the 14 consecutive days coinciding with active treatment. EMA prompts will be sent at randomly selected times between 8 AM and 11 PM. EMA prompts will assess mood state, suicide ideation, PTSD symptom severity, emotion regulation strategies, location, and social context.

**4.3.1. Mood state** will be measured using a short form of the Positive and Negative Affect Scale (PANAS), a self-report scale that assesses positive and negative emotional states. Respondents are directed to rate the extent to which they are currently experiencing positive emotions and negative emotions.

**4.3.2. Suicide ideation** will be assessed using the first 5 items of the Scale for Suicide Ideation (SSI), described above in Section 4.1.1. The first 5 items assess intensity of the wish to live, wish to die, balance of the wish to live and wish to die, active suicide ideation, and passive suicide ideation.

**4.3.3. PTSD symptom severity** will be assessed using the NSESS, described above in Section 4.2.1.

**4.3.4. Location** will be assessed with a checklist that directs subjects to indicate their current location: home, work, school, friend's residence, family member's residence, bar/tavern/pub, indoor public space (e.g., grocery store, shopping center, gym), or outdoor public space (e.g., park, swimming pool). These items were selected to assess subjects' physical location.

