#### 4.4. Covariates

**4.3.1. Psychiatric diagnosis** will be measured using a combination of (a) the Diagnostic Interview for Anxiety, Mood, and OCD and Related Neuropsychiatric Disorders (DIAMOND), (b) the American Psychiatric Association Disorder-Specific Severity Measures, and (c) the Adjustment Disorder New Module 8.

**4.3.1.1. Diagnostic Interview for Anxiety, Mood, and OCD and Related Neuropsychiatric Disorders (DIAMOND).** The DIAMOND is an empirically-supported structured diagnostic interview that assesses the most common mood, anxiety, and trauma-related psychiatric disorders in mental health.

**4.3.1.2. American Psychiatry Association (APA) Disorder-Specific Severity Measures.** The APA Disorder-Specific Severity Measures include a collection of self-report scales that assess the frequency of symptoms associated with commonly occurring psychiatric disorders. In the present study, we will use the Disorder-Specific Severity Measures for depression, specific phobia, social anxiety disorder, panic disorder, agoraphobia, generalized anxiety disorder, dissociative symptoms, and substance use.

**4.3.1.3. Adjustment Disorder New Module 8 (ADNM-8).** The ADNM-8 is an 8-item self-report scale that assesses recent exposure to a range of non-traumatic life stressors (e.g., divorce/separation, family conflicts) and frequency of symptoms associated with an adjustment disorder.

[figure not shown]
**4.3.2. Trauma exposure** will be measured using the Life Events Checklist for DSM-5 (LEC-5), an 18-item self-report scale that assesses exposure to a range of potentially traumatic events, and several features of the most stressful or upsetting event (e.g., potential for injury or death, involvement of sexual violence).

Assessment Measures	Screen	Eligibility	Pre-Tx	Tx	FU1	FU2
					Week	
			1	1-2	26	52
Primary Outcomes						
Scale for Suicide Ideation	S	I	E	E	S	S
Self-Injurious Thoughts and Behaviors Interview-Revised	S	I	E	E	S	S
Secondary Outcomes						
National Stressful Events Survey PTSD Short Scale	S	I	E	E	S	S
DSM-5 Self-Rated Level 1 Cross-Cutting Symptom Measure	S				S	S
Scales of Psychological Well-Being	S				S	S
Covariates						
Severity Measure for Depression	S					
Severity Measure for Social Anxiety Disorder	S					
Severity Measure for Specific Phobia	S					
Severity Measure for Panic Disorder	S					
Severity Measure for Agoraphobia	S					
Severity Measure for Generalized Anxiety Disorder	S					

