## 5. Detailed Study Procedures

The flow of participants through the study procedures are displayed in the figure below:

Potential participants will be recruited via a combination of methods outlined above in Section 3.2.1 and will complete an initial self-report screening to assess for the presence and intensity of psychological symptoms associated with PTSD and other common comorbid conditions (e.g., depression, panic disorder), and presence and intensity of suicide ideation. Potential participants will also be asked about their military service history. The entire screening process is expected to take less than 30 minutes to complete. Based on their responses to survey items, potential participants may be invited to share their contact information, which will be emailed to a member of the research team.

A researcher will then contact the potential participant to complete an eligibility interview conducted by phone or Zoom. During this interview, clinician-administered interviews will be completed to confirm the potential participant's primary diagnosis, to assess level of suicide risk (i.e., determining if there is imminent risk warranting immediate intervention and assistance), and to confirm prior military service. Individuals meeting eligibility criteria will then be given additional information about the study procedures and will be able to ask any questions about the study's procedures. The eligibility interview is expected to take approximately 1 hour to complete.

Those agreeing to continue their participation will be assisted in downloading the EMA data collection app to their smartphone, and will receive instructions on how to use the app. Finally, they will be

randomized to one of the two treatment groups and scheduled for their first therapy session. Participants will participate in one hour of psychological treatment per day for 12 consecutive business days (i.e., excluding weekends), for a total time commitment of 12 hours. They will also complete EMA surveys every day for 14 consecutive days (i.e., including weekends). EMA assessments will require 20 minutes per day, for a total of approximately 4.5 hours.

After completing treatment, participants will be given instructions on how to remove the EMA data collection app from their smartphones. Participants will be contacted 6 and 12 months postbaseline to complete the scheduled follow-up assessments. Each follow-up assessment is expected to take approximately 15 minutes to complete.

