## **6. Data Analysis**

Prior to statistical analyses, we will visually inspect data to ascertain distributional properties and determine if data meet the assumptions for each of our planned analyses. Based on our previous studies, we expect the primary outcome (suicide ideation) to be positively skewed. If true for this study, we will consider and evaluate the most appropriate method for approaching each analysis (e.g., data transformations, bootstrapped confidence intervals, use of generalized linear modeling). We anticipate having up to 50% missing data from EMA and up to 30% missing data from follow-up. We will first use Little's test to determine if the missing data are ignorable (i.e., missing completely at random or missing at random). If the missing data are not ignorable, we will use multiple imputation. The number of imputed datasets will be determined based on the percent of data that are missing and contemporary recommendations. Our primary outcome for Aim 1 is suicide ideation, measured using the SSI total score.

For H1, we will use generalized linear mixed models with SSI total score as the outcome variable and treatment, time, and treatment x time entered as predictors. We will first assess change in SSI scores across the four primary time points: baseline, posttreatment, 6 months, and 12 months. H1 will be supported if there is a statistically significant treatment x time interaction indicating a faster reduction in suicide ideation among participants receiving CPT+CRP. Sensitivity analyses will then be conducted with SSI total scores from the initial screening and the eligibility interview added to the model, thereby enabling us to determine if reductions in suicide ideation coincided with the start of treatment and ruling out the possibility that observed differences between groups is attributable to pre-treatment temporal trends (e.g., participants in one group showing reductions in suicide ideation that precede the initiation of treatment).

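### The primary model needs a full SSI total at the end of treatment, but the schedule and Section 5 provide none, and the baseline total is not named

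*Combined protocol and SAP*

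**What the plan says.** Section 6 fixes the outcome: "Our primary outcome for Aim 1 is suicide ideation, measured using the SSI total score". For H1 it then states: "We will first assess change in SSI scores across the four primary time points: baseline, posttreatment, 6 months, and 12 months". H2 repeats that model in participants with ideation at baseline. Section 3.8 gives the same plan in weeks: "The primary outcome, suicide ideation, will be assessed up to 4 times: baseline, 2 weeks, 26 weeks, and 52 weeks".

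The schedule table at the end of Section 4.4 has the columns "Assessment Measures Screen Eligibility Pre-Tx Tx FU1 FU2", and the outcome's row reads "Scale for Suicide Ideation S I E E S S". The key gives S as self-report, I as interview and E as EMA. Section 4.3.2 says that ideation in EMA "will be assessed using the first 5 items of the Scale for Suicide Ideation (SSI), described above in Section 4.1.1". Under Section 4.1.1 everyone answers five items, and those who endorse item 4 or 5 answer 14 more. Section 6 analyses the five-item EMA sum in a model of its own.

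In Section 5, once treatment ends, "participants will be given instructions on how to remove the EMA data collection app from their smartphones". The next step described is: "Participants will be contacted 6 and 12 months postbaseline to complete the scheduled follow-up assessments".

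On baseline, Section 6 brings the screening and eligibility totals in only as a sensitivity analysis. Section 3.7 stratifies randomisation on endorsement of SSI item 4 or 5 for the past week.

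**The concern.** The analysis sections require a measurement that the operational sections do not schedule. Staff work from the schedule and the procedures. If they follow those, the primary model has no SSI total from the start of treatment until week 26, which is 24 weeks after the week-2 point in Section 3.8.

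That interval matters to this trial's own rationale. Section 2 cites faster decline in ideation with the crisis response plan. It also cites CPT studies in which ideation worsened again some months after therapy (a statement about CPT itself, not about a difference between arms). Without an end-of-treatment total, the primary outcome cannot distinguish ideation that never fell from ideation that fell and came back. A total that was not collected cannot be recovered later.

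The baseline is a second, smaller gap. The primary model, the H2 subgroup and the exploratory comparison all depend on a baseline score, and no visit is named as its source.

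**Working it through.** **1. Primary time points against scheduled totals.**

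| Point in Section 6 | Schedule entry for the SSI | Full total available? |
|---|---|---|
| Baseline | Screen: self-report; Eligibility: interview; Pre-Tx: EMA | Two candidates, none named |
| Posttreatment (week 2 in Section 3.8) | No column; Tx, weeks 1-2: EMA | No |
| 6 months | FU1, week 26: self-report | Yes |
| 12 months | FU2, week 52: self-report | Yes |

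So 2 of 4 points have a scheduled total, 1 has candidates but no named source, and 1 has none. Section 5, read on its own, gives the same result for posttreatment.

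**2. Can EMA stand in?** Only partly. The full scale has 5 + 14 = 19 items. For someone who denies items 4 and 5, the five EMA items are the whole scale as administered. For someone who endorses either, 14 of the 19 items are absent. Section 3.8 expects 50-70% to report ideation at baseline, so EMA is incomplete chiefly in the H2 population. Section 6 also allows for up to 50% missing EMA data.

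**3. Which score is baseline?** If the screening and eligibility totals are additions to the four-point model, neither is one of the four. The only other pre-treatment SSI entry is EMA, which is not a total and which Section 4.3 places during active treatment. However, Section 5 puts randomisation before the first session, and Section 3.7 stratifies on items 4 and 5. A pre-randomisation score must therefore exist.

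**4. Are week 2 and posttreatment the same visit?** Section 3.5 gives a 14-day span. Section 5 gives twelve business days in a row, which cover 16 calendar days (Monday to Thursday start) or 18 (Friday start), ignoring holidays. The two statements do not agree.

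**5. The stated power.** Inputs from Section 3.8: two-sided alpha 0.05, r = 0.1, d = 0.3. Assumed here: f = d/2 = 0.15, sphericity, categorical time, and 112 read as the total. With m assessments, λ = f²·N·m/(1 − r), df1 = m − 1 and df2 = (N − 2)(m − 1).
- N = 112, m = 4: λ = 0.0225 × 112 × 4/0.9 = 11.2; power 80.7% (stated 80%).
- N = 150, m = 3: λ = 0.0225 × 150 × 3/0.9 = 11.25; power 85.7% (stated 86%).
- Attrition: 112/(1 − 0.25) = 149.3, so 150.

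The plan's figures reproduce.

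**6. Does dropping posttreatment lower power?** Three assumed profiles of the arm difference δ over weeks 0, 2, 26 and 52 were each scaled to f = 0.15 on four points. The omnibus test uses λ = N·Σ(δ − mean δ)²/[4(1 − r)]. The straight-line slope in weeks, with centred times c, uses λ = N·(Σcδ)²/[4(1 − r)·Σc²]. Power at N = 112, with and then without posttreatment:

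| Profile | Omnibus | Slope |
|---|---|---|
| Constant (0, 1, 1, 1) | 80.7% to 80.8% | 44.6% to 77.7% |
| Linear in weeks (0, 2, 26, 52) | 80.7% to 73.8% | 91.6% to 82.7% |
| Fading (0, 1, 0.5, 0.25) | 80.7% to 27.6% | 11.6% to 12.5% |

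The direction depends on the profile and on how time is coded.

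**The case against.** The strongest reply is that the plan does intend the assessment. Sections 3.8 and 6 both name it, Section 5 is silent rather than contrary, and a form at the last session is compatible with follow-up contacts at 6 and 12 months. The participant-flow figure in Section 5, where such a visit might be drawn, is not visible.

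The schedule is also an imperfect witness:
- It codes the eligibility SSI as interview, although Section 4.1.1 calls the scale self-report.
- It codes the suicidal-behaviour measure as EMA, although Section 4.3 does not list that content.
- It shows EMA at Pre-Tx, although Section 4.3 ties EMA to active treatment.
- It omits the CAPS-5 and the DIAMOND.

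These points stand, and they lower confidence that the total would in fact be missed. They do not remove the disagreement between the analysis sections and the operational ones.

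Three stronger readings are tempting, and the documents do not support them.
- **The trial loses power.** A reader might point to the fall to 27.6%. That figure rests on an assumed fading profile whose posttreatment difference, scaled as above, is 0.81 SD, outside the 0.3-0.7 range in Section 3.8. Section 3.8 also describes the primary analyses as slope comparisons, and under a straight-line slope two of the three profiles gain power.
- **Early change goes unmeasured.** The five-item EMA sum does measure it, and Section 6 lets that interaction support H1 as well. What is missing is the primary outcome, the full total.
- **The H2 subgroup cannot be defined.** Section 3.7 already supplies an ideation rule and implies a pre-randomisation score. What is open is which score is used and whether H2 uses that stratum.

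**Conclusion.** The inconsistency is real and concerns the primary analysis. One of its four time points has no full SSI total in the schedule or in Section 5, and the baseline total is unnamed. If the operational sections are followed as written, there is no full total between the start of treatment and week 26.

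The conclusion rests on the schedule and Section 5 together, and on EMA being limited to items 1-5. That the text conflicts is certain; that the total would go uncollected is held with moderate confidence. That the primary baseline is neither the screening nor the eligibility score is an inference from the sensitivity analysis, not a stated fact. No loss of power is claimed.

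**What to change.** - Add a posttreatment column to the schedule, and a step in Section 5, for the full self-report SSI.
- Name one full SSI total collected before randomisation as the primary-model baseline, either screening or eligibility, and state how it is administered. Limit the sensitivity analysis to the other one. A new form just before the first session could fall after randomisation and would then be a poor basis for the H2 subgroup.
- Define the H2 subgroup and the exploratory comparison by the item 4/5 classification used for stratification in Section 3.7.
- Keep the five-item EMA sum as its separate analysis.
- Make Sections 3.8, 5 and 6 and the schedule agree. Reconcile the treatment-length statements in Sections 3.5 and 5, so that week 2 and posttreatment denote the same visit.

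The cost is one self-report form at one occasion for the 150 randomised participants (5 items, or 19 if item 4 or 5 is endorsed), one schedule column and wording changes. Naming the baseline needs no new data.
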